10.5 Vital Signs

The following parameters will be summarized by each timepoint and change from baseline with number of subjects, mean, standard deviation, median, minimum, and maximum by vaccination group.

- Vital Sign parameters: Systolic blood pressure (mmHg), Diastolic blood pressure (mmHg), Heart rate (beats/min), Respiratory rate (breaths/min), Body temperature (°C)

11. Immunogenicity Analysis

Immunogenicity analysis will be performed on mITT, PP with sufficient sample to assay.

The immunogenicity parameters are as follows.

Table 6 In the immunogenicity evaluation category, positivity is classified according to the following criteria.

Immunogenicity			
Endpoints	Parameter	Unit	Criteria for Positive/Negative (or Responder/Non-Responder)
Binding antibody	S-ELISA	Endpoint Titer	Threshold limit to be considered as having a positive response is >50
	ORF3a-ELISA	Endpoint Titer	Threshold limit to be considered as having a positive response is >50
Neutralizing antibody	NEUT	NT ₅₀	Cutoff value on a per-subject basis is defined as: 4x that subject's Day 0 response.
T cell response	ELISPOT	SFU per 10 ⁶ cells	Cutoff value on a per-subject basis is defined as: 2x that subject's Day 0 response. If there is no Day 0 data for that subject, then the cutoff is defined as 2x average Day 0 response for all study participants

CONFIDENTIAL

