9.2 Immunogenicity assessments

9.2.1 SARS-CoV-2 Binding ELISA

Standardized ELISA assays will be performed to measure the anti-SARS-CoV-2 S and ORF3a binding antibody responses. Samples will be scored as positive if the average optical density (OD) is greater than 0.10 absorbance units and greater than the average OD before immunization plus 2.5 times the standard deviation (SD) of the OD before immunization at the same dilution. Results will be presented as the geometric mean titer (GMT) of the antibody titer, end-point titer, i.e. the last dilution where the OD value is above the calculated threshold.

The definition of seroconversion as a positive response post-baseline at the lowest dilution tested (i.e. and antibody titer that is below 1:100 at baseline and after vaccination positive at or above the 1:100 dilution) assuming that the baseline response would be negative at 1:100. The criteria for the appropriate immunogenicity of the SARS-CoV-2 binding antibody is planned to have a positive response rate of 70% or more in each group at the interim analysis.

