2.2 Immunogenicity Endpoints

- Evaluation of GMT and serum conversion rates of SARS-CoV-2 Spike and ORF3a protein-specific binding antibodies induced by GLS-5310 (the end-point titer of binding antibodies in serum at each timepoint)
- Evaluation of GMT and positive responder rate of neutralizing antibody responses induced by GLS-5310 (plaque-reduction neutralizing titer, PRNT in serum at each timepoint)
- Evaluation of positive responder rate of T cell response induced by GLS-5310 (antigen-specific interferon – gamma (IFN- γ) secretion T-cell response in PBMC at each timepoint)

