Intention to treat (ITT) will include all participants who sign informed consent.

✓ **Modified Intention to treat (mITT)**

Modified intention to treat (mITT) will include all participants who sign informed consent and who have received at least one administration of investigational product. The mITT will be the primary analysis population for baseline and demographic assessments and efficacy outcomes. All subjects will be summarized based on the treatment group to which they were assigned. Since not all subjects will have evaluable immune response data, analysis of immune responses will be performed only for available samples.

✓ **Safety Set (SS)**

Safety Set (SS) will include all mITT participants. The SS will be the primary population for summary and analysis of safety assessments. All subjects will be summarized based on the treatments that actually received.

✓ **Per-Protocol Set (PPS)**

Per-Protocol Set (PPS) will include all mITT participants who complete the trial by receiving all

CONFIDENTIAL

vaccinations and have no significant protocol violations. This set will be used as a sensitivity analysis to summarize the primary and secondary response outcomes. For secondary and exploratory assessments of antibody and T cell immune responses, denominators will include only those participants who are SARS-CoV-2 seronegative at baseline. Unevaluable samples will not be considered as part of the denominator at relevant time points.

Protocol violations that can be excluded from the analysis group include the following and are defined according to the analysis population's definition of 'SOP 0406'.

- Participants who have never been vaccinated with all vaccinations
- Positive for SARS-CoV-2 serum test at Baseline
- Inclusion/Exclusion criteria violation
- Contraindicated drug administration
- Randomization errors
- Vaccination errors
- No blood draw for immunogenicity assessment

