8.4 Derived or transformed variables

The baseline is defined as last non-missing value on or prior to the start date of IP administration.

Table 4 Derived Variables

Variables	Method
Change from baseline	Post-baseline value – Baseline value
Age group	Age < 66y old, Age \geq 66y old
Total dose (mg)	Sum of investigational product doses at each time point
GMT	$10^{\text{Mean of log}_{10} \text{ value}}$

CONFIDENTIAL

Variables	Method
Change from baseline (GMT)	$10^{(\text{Mean of } (\log_{10} \text{post} - \text{baseline value} - \log_{10} \text{baseline value}))}$
GMR	$10^{(\log_{10} \text{GMT1} - \log_{10} \text{GMT2})}$
AE Duration (days)	AE end date – AE start date+1 if AE end date is ongoing, replaced with last visit date and add symbol (\geq) (ex. ≥ 15)
Occurrence Duration (days)	AE start date – Investigational product start date

9. Subject Information

Subject information will be analyzed on ITT.

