11.1 Binding Antibody Responses

The binding antibody response will be classified as responder/non-responder and will be analyzed as the frequency of responses for each assay for each treatment arm at each time point at which an assessment is performed. Estimates of proportions and exact 95% Clopper-Pearson's confidence interval and exact 95% confidence interval (Chan and Zhang 1999) for the differences between the groups will be calculated. Comparison between treatment arms will be carried out using a Fisher's exact test. However, Part 1 of the study is not powered to distinguish statistical differences between dosing regimens.

The group geometric mean titer (GMT) for binding antibody endpoint titers for the SARS-CoV-2 will be calculated and the 95% confidence interval will be presented. The comparison among the administration groups of GMT will be analyzed using a two-sample t-test. Also, the geometric mean titer ratio will be calculated and its 95% confidence interval will be provided. For the GMT and the mean fold increase in GMT from baseline, the mean of the antibody that was transformed by log10 and the 95% confidence interval will be calculated and then changed back to the original unit.

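### The SAP keeps binding-antibody seroconversion as an endpoint but scores it as endpoint titre >50 with no Day 0 condition, so baseline-positive participants count as responders

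*SAP*

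**What the plan says.** Protocol synopsis and 9.1: the seroconversion rate for Spike and ORF3a binding antibody is, with the GMT, the immunogenicity part of the primary endpoint.

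Protocol 9.2.1: seroconversion is a positive post-baseline response at the lowest dilution tested, explained as an "antibody titer that is below 1:100 at baseline and after vaccination positive at or above the 1:100 dilution", and this is done "assuming that the baseline response would be negative at 1:100".

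SAP 2.2 keeps the endpoint: "Evaluation of GMT and serum conversion rates of SARS-CoV-2 Spike and ORF3a protein-specific binding antibodies induced by GLS-5310". SAP 4.1 makes a seroconversion rate above 70% a condition for entering Phase IIa.

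SAP 11, Table 6, gives the only scoring rule for S-ELISA and ORF3a-ELISA: "Threshold limit to be considered as having a positive response is >50". SAP 11.1 applies it: "The binding antibody response will be classified as responder/non-responder and will be analyzed as the frequency of responses". In the same table, the neutralisation and ELISPOT cut-offs are multiples of the Day 0 response.

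SAP 8.4 defines baseline ("The baseline is defined as last non-missing value on or prior to the start date of IP administration"), but Table 4 derives no seroconversion variable from it.

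SAP 6 on populations: "The mITT will be the primary analysis population for baseline and demographic assessments and efficacy outcomes". Only the per-protocol set lists "Positive for SARS-CoV-2 serum test at Baseline" as a reason for exclusion. The seronegative-only denominator in that paragraph is stated for secondary and exploratory assessments, and binding antibody is primary. Protocol 11.1 also calls for separate assessment of participants seropositive at baseline. SAP 6 does not repeat this, and SAP 12 sets aside the related boosting objective as already analysed.

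SAP 12 lists only exploratory items as changes from the protocol.

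**The concern.** The protocol's definition has two conditions, one at baseline and one after vaccination. The SAP implements only the second. A programmer who follows Table 6 and 11.1 scores a participant with a positive Day 0 titre who stays positive as a responder. The resulting proportion is the share who are seropositive at the visit, while SAP 2.2 calls it a conversion rate. At stake are the meaning of each arm's rate and its Clopper-Pearson interval, for a primary endpoint.

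The protocol does not rule baseline positives out. Exclusion 22 bars a positive screening test, but 7.3.7 allows that test to be PCR or antibody, so a PCR-only screen leaves serostatus unknown. Protocol 2.4 plans an analysis of participants who are seropositive at baseline.

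**Working it through.** **1. The plan's own figure.** The synopsis claims 80% power for a 14-point difference in seroconversion at N=126, randomised 2:1 (84 v 42). Neither the placebo rate nor the sidedness is given. I take two-sided alpha 0.05 and the pooled normal approximation, power = Φ[(Δ − 1.96·SE₀)/SE₁].

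- With placebo at 0%, the pooled rate is 84×0.14/126 = 0.0933. SE₀ = √(0.0933×0.9067×(1/42+1/84)) = 0.0550 and SE₁ = √(0.14×0.86/84) = 0.0379.
- Power = Φ[(0.14 − 0.1078)/0.0379] = Φ(0.85) = 80.3%. The figure reproduces.
- With placebo at 2% or 5%, power for the same 14 points is 69.0% or 57.4%.

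So, at low placebo rates, the stated power needs a placebo rate near zero. That is natural for conversion; seropositivity does not guarantee it. The point does not rest on this figure.

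**2. The two rules side by side**, for a participant with both titres:

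| Day 0 | After vaccination | Protocol 9.2.1 | SAP Table 6 |
|---|---|---|---|
| negative | positive | converter | responder |
| negative | negative | no | no |
| positive | positive | not a converter | responder |
| positive | negative | no | no |

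They differ only in the third row.

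**3. Size.** Inputs: Phase IIa arms of 80 and 40 and Phase I arms of 15 (protocol Table S1). True conversion among baseline negatives is set at p = 70%, the level of the Phase IIa entry criterion. The baseline-positive share s is not in the documents; 1%, 2% and 5% are assumed. I also assume that every baseline positive stays positive and that no placebo participant converts.

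- SAP rule: vaccine s + (1−s)p; placebo s; difference (1−s)p.
- Protocol condition, Day 0-negative participants: vaccine p; placebo 0; difference p.
- Vaccine-arm excess of the SAP rule: s + (1−s)p − p = s(1−p). Placebo excess: s.

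| s | SAP vaccine | SAP placebo | Day 0-negative vaccine | Vaccine excess | SAP difference |
|---|---|---|---|---|---|
| 1% | 70.3% | 1% | 70% | 0.3 points | 69.3 points |
| 2% | 70.6% | 2% | 70% | 0.6 points | 68.6 points |
| 5% | 71.5% | 5% | 70% | 1.5 points | 66.5 points |

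The placebo rate rises by more than the vaccine rate, so the SAP difference is slightly below the 70 points seen in baseline negatives.

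**4. One person.** 1/80 = 1.25 points in arm 2b, 1/40 = 2.5 points in arm 2a, and 1/15 = 6.7 points in a Phase I arm. In an arm of 15, 10/15 = 66.7% and 11/15 = 73.3% lie on either side of 70%.

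**5. Power.** Exact two-sided Fisher test at 0.05, 80 v 40, p = 70%, s = 1–5%: above 99.9% under the SAP rule. It is also above 99.9% under the protocol definition on the whole mITT with baseline positives as non-converters, (1−s)p v 0.

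**The case against.** The best defence is that Table 6 already applies 9.2.1. That section leads with a positive post-baseline response, and the baseline clause explains it under an assumption that baseline is negative. If the assumption holds, positivity after vaccination is seroconversion. This stands as far as it goes: with no baseline positives, the two rules give the same result. But the SAP neither carries the assumption over nor checks it in its primary set.

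Other points stand and limit the concern:

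- Exclusions 22, 23 and 29 (positive test or known infection, contact with cases, prior COVID-19 vaccination) should keep s small.
- The ELISA threshold in 9.2.1 is built on pre-immunisation OD. If it is set per subject, a positive Day 0 titre is nearly impossible and s is near zero. The text does not say whether it is per subject or pooled.
- Protocol 11.4 provides for responder analysis, and 9.2.1 words its own 70% criterion as a positive response rate, so the protocol is not uniform.
- SAP 11.1 also gives the fold rise in GMT from baseline.
- The SAP contents list a TLF shell that is not in the supplied text, so the final table layout cannot be seen.

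A reader might infer that baseline positives are hidden. They are not: SAP 11.1 reports each time point and SAP 9.4.1 tabulates baseline PCR/antibody results.

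A reader might also infer that the cut-offs differ. The documents do not show this: >50 and ≥1:100 agree if a sample negative at 1:100 is coded 50 or less, and the coding is not stated.

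**Conclusion.** The gap is real and minor. As written, the SAP rate is seropositivity unless no mITT participant is positive at Day 0. The textual mismatch is certain; its size is not known. At 70% true conversion and an assumed s of 1–5%, the vaccine rate is 0.3–1.5 points above the rate in baseline negatives, and placebo shows 1–5% instead of 0%.

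Four stronger readings are tempting and unsupported:

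- *The comparison favours vaccine.* It does not. The arm difference is (1−s)p, slightly below p.
- *Each arm's rate is too high by s.* That follows only if baseline positives are scored as non-converters on the whole mITT. No passage says so, and protocol 11.1 points to assessing them separately.
- *Power is lost.* At 70% it is not. At a true rate of 14%, power under the SAP rule would fall from 80.5% at s = 0 to 69%, 61% and 47% at s = 1%, 2% and 5%. But the chance of 11 or more of 15 at a 14% rate is about 3 in 10 million, so 14% is implausible after the entry criterion. SAP 5 also says the trial tests no hypotheses.
- *Phase IIa was entered on the wrong rule.* SAP 4.1 reports that interim in the past tense, and the documents do not show which rule was used.

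**What to change.** In SAP Tables 4 and 6, derive seroconversion separately for S and ORF3a as Day 0 titre <1:100 and post-vaccination titre ≥1:100. Use it for the proportions, confidence intervals and Fisher test in 11.1.

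- Denominator: Day 0-negative mITT participants with evaluable samples. Report baseline positives separately by arm, as protocol 11.1 foresees. Add a supplementary all-mITT display that counts them as non-converters.
- Missing Day 0 titre: leave as missing, in line with protocol 11.7 and SAP 8.1, and report how many there are.
- State the value coded for a sample negative at 1:100.
- If titre >50 is also reported, label it seropositivity and list it in SAP 12.

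The cost is SAP wording and one derived flag per antigen, from Day 0 serum already in the schedule. The downside is a slightly smaller denominator, or a slightly lower reported rate, if anyone is baseline-positive.

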Primary study endpoints– Phase I & IIa: 
• Evaluate the adverse events (Toxicity Grading Scale for Healthy Adult and Adolescent Volunteers Enrolled in Preventative Vaccine Clinical Trials)• Determine of GMT and seroconversion rate of SARS-CoV-2 Spike and ORF3a protein specific binding antibody responses induced by GLS-5310 relative to treatment arm (Endpoint titer of binding antibody in serum at each timepoint)
Secondary study endpoints– Phase I & IIa: 
• Determine the positive responder rate of T cell responses induced by GLS-5310 (Antigen-specific interferon gamma (IFN-γ) secretion T-cell response in PBMC at each timepoint)• Determine of GMT and positive responder rate of the neutralizing antibody response induced by GLS-5310 (plaque-reduction neutralizing titer in serum at each timepoint)

Exploratory study endpoints**Phase I**

- Determine binding antibody responses after a single dose of vaccine related to treatment arm (Endpoint titer of binding antibody in serum at each timepoint)
- Determine whether passive transfer of human serum can protect against pulmonary infection from SARS-CoV-2 challenge in an animal infection model (Survival rate, blood and viral load measurement of major organs, pathological examination of respiratory/lung area, immunogenicity evaluation)

Phase IIa

- Determine the persistence of immune responses following vaccination with GLS-5310 (Endpoint titer of binding antibody in serum at each timepoint, Antigen-specific interferon gamma (IFN- γ) secretion T-cell response in PBMC at each timepoint, plaque-reduction neutralizing titer in serum at each timepoint)
- Determine the extent of immune boosting for participants who are seropositive at baseline following vaccination with GLS-5310 (Endpoint titer of binding antibody in serum at each timepoint, Antigen-specific interferon gamma (IFN- γ) secretion T-cell response in PBMC at each timepoint, plaque-reduction neutralizing titer in serum at each timepoint)
- Determine whether immune responses to GLS-5310 of participants age 66-85 years differ from those age 65 years and younger.

Table S1: Dosing arms and treatment regimen

Study Phase	Study Arm	N	Route	GLS-5310 Dose	Vaccination schedule	Table of events
1	1a	15	ID	0.6 mg	0 – 8 weeks	S2
1	1b	15	ID	1.2 mg	0 – 8 weeks	S2
1	1c	15	ID	1.2 mg	0 – 12 weeks	S3
2	2a	40	ID	Placebo	0 – 8 weeks	S2
2	2b	80	ID	1.2 mg	0 – 8 weeks	S2

Study design:

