9.2.3 SARS-CoV-2 ELISpot

Cellular immune responses will be assessed by measuring the number of SARS-CoV-2 antigen-specific IFN- γ secreting peripheral blood mononuclear cells (PBMCs) as determined by IFN- γ ELISpot assays. Cell responses to stimulation with SARS-CoV-2 peptides using 15-mer peptides overlapping by 10 amino acids spanning the entire S and ORF3a proteins will be measured and results reported as spot forming units per million cells (SFU/ 10^6 PBMC). Positive response cutoff calculations will include at least a fold-rise from subject-specific baseline SFU/ 10^6 PBMC values, based upon assay optimization criteria. The criteria for the appropriate immunogenicity of the SARS-CoV-2 T cell response is planned to have a positive response rate of 70% or more in each group at the interim analysis.

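### The ELISpot responder rule in SAP Table 6 is a bare 2-fold rise over Day 0 with no absolute floor, so at near-zero baselines counting noise is scored as a T-cell response

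*SAP*

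**What the plan says.** The T-cell responder rate is a secondary endpoint in both phases. The protocol synopsis lists it as "Determine the positive responder rate of T cell responses induced by GLS-5310".

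Protocol 9.2.3 describes the cutoff in general terms: "Positive response cutoff calculations will include at least a fold-rise from subject-specific baseline" values, based on assay optimization criteria. It names neither the fold nor any further condition. It also sets a benchmark: "T cell response is planned to have a positive response rate of 70% or more in each group at the interim analysis".

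SAP section 11, Table 6, supplies the operative rule: "Cutoff value on a per-subject basis is defined as: 2x that subject's Day 0 response". Where a participant has no Day 0 value, "then the cutoff is defined as 2x average Day 0 response for all study participants". SAP 11.3 then compares responder proportions by arm and time point, with exact confidence intervals and Fisher's exact test. It adds nothing to the definition.

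The binding-antibody rows of the same table use a fixed titre threshold (above 50). The protocol's ELISA rule (9.2.1) joins an absolute optical-density minimum of 0.10 to a margin of 2.5 SD over pre-immunization values. The ELISpot row has no such element.

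**The concern.** A cutoff that is a pure multiple of Day 0 shrinks with Day 0. At a Day 0 count of zero the cutoff is zero. One spot then makes a responder if the cutoff must be exceeded, and no spots at all are enough if it need only be reached. With one or two spots at Day 0, ordinary counting variation crosses the line often.

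Low Day 0 counts are plausible because the protocol excludes people with prior infection, a positive screening test or prior COVID-19 vaccination. That is an inference, since no Day 0 values are reported.

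At stake is the meaning of the reported responder rates. False responders raise the rate in every arm. In Phase IIa they also dilute the vaccine-placebo difference. Phase I has no placebo arm, so nothing there would reveal the inflation.

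**Working it through.** The documents state no false-positive rate, power or Day 0 distribution for this endpoint, so there is no figure of theirs to reproduce.

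**Inputs from the documents.** The 2x rule (SAP Table 6); 15 participants per Phase I arm; 40 placebo and 80 vaccine in Phase IIa (Protocol Table S1).

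**Assumptions not in the documents.** 0.6 million cells read per antigen (for example three wells of 200,000); Poisson noise only; the same true level before and after dosing; backgrounds of 2 to 50 SFU per million.

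**Formula.** The expected spot count is μ = background × 0.6. With Day 0 count B and post-dose count X independent Poisson(μ), the false-responder rate is f = Σ P(B=b) × P(X > 2b).

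Example at 2 SFU (μ = 1.2):
- b = 0: 0.3012 × 0.6988 = 0.2105
- b = 1: 0.3614 × 0.1205 = 0.0436
- b = 2: 0.2169 × 0.0077 = 0.0017
- larger b adds less than 0.0001, so f = 25.6%

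Most of this comes from the 30% of participants whose Day 0 count is zero.

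**Effect on reported results.** If the true responder rate is p with vaccine and 0 with placebo, the vaccine arm shows p + (1 − p)f, placebo shows f, and the difference is p(1 − f). For p = 60%:

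| Background (SFU per million) | μ | f, rule >2x | f, rule ≥2x | True 60% shows as | True 60-point difference shows as |
|---|---|---|---|---|---|
| 2 | 1.2 | 25.6% | 43.1% | 70.2% | 44.7 |
| 5 | 3 | 18.3% | 26.9% | 67.3% | 49.0 |
| 10 | 6 | 11.2% | 15.6% | 64.5% | 53.3 |
| 20 | 12 | 4.7% | 6.3% | 61.9% | 57.2 |
| 50 | 30 | 0.5% | 0.6% | 60.2% | 59.7 |

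The last two columns use the >2x rule. Expected false responders among 40 placebo recipients are 40f: about 10 at 2 SFU, 4 to 5 at 10 SFU and 2 at 20 SFU.

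**The 70% benchmark with 15 per arm.** 0.70 × 15 = 10.5, so 11 responders are needed. At a true 60% the chance of 11 or more is 22% with no false responders, 34% at the 10 SFU rate and 52% at the 2 SFU rate.

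**Phase IIa contrast.** For true rates of 25% against 0%, the power of Fisher's test (40 against 80, two-sided 5%) falls from 99.9% to 79.3% at f = 10% and 59.5% at f = 20%.

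**Which remedy works** (0.6 million cells, illustrative values):
- At least 2x Day 0 and also at least 10 SFU: 13.5% false responders at a 10 SFU background. This barely helps.
- At least 2x the larger of Day 0 and 10 SFU: 1.3% at a 10 SFU background, but 5.7% at 20 SFU. The floor has to suit the background.
- At least 2x Day 0 and a rise of at least 20 SFU (12 spots): below 0.1% at 2, 5 and 10 SFU, and 1.0% at 20 SFU.

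**The case against.** The strongest reply is that the premise is unseen. No Day 0 count, cell number or background is given, and at 20 to 50 SFU the problem is small. Protocol 7.5 refers to pools of peptides for each antigen. If pool counts are summed, more spots are read: at a 10 SFU background, 1.2 million cells give 4.7% and 2.4 million give 1.0%. Background subtraction or replicate-well rules may also sit in assay documents outside the plan. All of this stands, so the size can only be given as a range. It does not supply the missing rule for a zero Day 0.

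Several stronger readings are tempting, and the documents do not support them:

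- **That the SAP contradicts the protocol.** Protocol 9.2.3 sets a fold-rise as the minimum and permits further criteria without requiring any. A 2x rule complies, and so would one with a floor.
- **That noise could carry the trial into Phase IIa.** The entry gate is binding-antibody seroconversion plus a safety count (Protocol 11.5, SAP 4.1). The 70% T-cell figure is a benchmark with no decision attached.
- **That false responses accumulate over follow-up.** Under the same model, at least one false response over six post-baseline visits would occur in 51, 40 and 28% at 2, 5 and 10 SFU. The SAP analyses each time point separately and plans no such cumulative count.
- **That noise favours the vaccine in Phase IIa.** It enters both arms and shrinks the contrast, and the placebo arm makes it visible.
- **That the neutralization rule ("4x that subject's Day 0 response") has the same defect.** A titre is not a spot count, and the Poisson figures do not apply. GMTs are computed on log10 values, so an undetectable titre must already carry some positive value. That value is simply not stated.

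The SAP also calls the trial exploratory and descriptive. This limits the consequence, but the responder rates are still to be reported and tested.

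**Conclusion.** The point holds as a weakness in a stated rule for a secondary endpoint. Table 6 makes the 2-fold rise the whole ELISpot definition. It leaves zero baselines and the choice of > or ≥ open, and it gives the missing-Day-0 fallback no floor either. When Day 0 is at or near zero, noise is counted as response.

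The size is conditional on the assumed cell number and noise model. It runs from serious (18 to 26% false responders per visit and antigen at 2 to 5 SFU per million) through moderate (11% at 10 SFU) to negligible (0.5% at 50 SFU). The main harm is to per-arm responder rates, above all in Phase I, with attenuation of the Phase IIa difference second. Correcting it is worthwhile and inexpensive. Nothing here shows that a trial decision turned on it.

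**What to change.** In SAP Table 6, define an ELISpot responder in one of two ways: a post-dose value of at least 2x the larger of Day 0 and a fixed floor, or a value of at least 2x Day 0 together with a fixed minimum rise in SFU per million. The first form settles a zero Day 0, and both settle the choice of inequality. Apply the same floor to the missing-Day-0 fallback, and state whether the S and ORF3a responses are scored separately.

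Take the floor or minimum rise from assay qualification data, such as the detection limit. The 10 and 20 SFU values above are illustrations only.

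Timing matters. SAP 4.1 describes the interim analyses in both phases as done, Phase I is open-label, and Phase IIa is unblinded at Visit 4. The value should therefore be set and documented without reference to post-dose results by arm. The current 2x rule should be reported alongside for consistency with the interim results. Show the placebo responder rate at each visit up to unblinding as an empirical false-positive rate.

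For neutralization, only state the value assigned to an undetectable Day 0 titre.

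The cost is a revised table cell, one extra table and no new data collection. Reported responder rates will be lower. If backgrounds are very low, the drop could match the inflation shown above (about 10 points at 2 SFU for a true 60%).
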